5.2.2 Rationale for Exclusion of HER2 Positive Population

Subjects with human epidermal growth factor receptor 2-positive disease are excluded from this trial. This rationale for excluding these subjects is that the current standard of care (SOC) for HER2 positive subjects is different than HER2 negative subjects and would require addition of trastuzumab to the induction chemotherapy choices. Inclusion of HER2 positive subjects would also result in an additional option for maintenance therapy and thus result in greater subject heterogeneity.

5.2.3 Rationale for Switching Subjects from Chemotherapy to Avelumab

The proposal to switch subjects assigned to the experimental arm after they have completed 12 weeks of chemotherapy is appropriate for the following reasons:

- There is no data supporting that additional chemotherapy beyond 4 to 6 cycles (up to 12 weeks of treatment) will result in improved survival in the context of a disease where it is common practice to re-induce patients at the time of disease progression. Patients who have not responded to or who will cease to respond to avelumab will be re-induced either with platinum-based doublets or with drugs that have shown clinical benefit as a second-line therapy. Subjects will be monitored every 6 weeks and rescue therapy may be administered once disease progression is established.
- Treatment of patients with avelumab has resulted in an ORR of 15% in patients with gastric cancer from Asian and non-Asian regions. Some of these responses were long lasting and a number of subjects with prolonged SD were also observed. Based on these data, it is reasonable to interrupt chemotherapy after 12 weeks to initiate an immunotherapy that has been reported to induce prolonged responses in advanced gastric cancer patients who will ultimately progress after initial chemotherapy regimens.
- For subjects randomly assigned to receive additional chemotherapy in the Maintenance Phase, it is recommended that the chemotherapy regimen does not to exceed 6 cycles. This is supported by the previously established regimen in the registration study for trastuzumab (TOGA). In conclusion, switching subjects after 12 weeks of chemotherapy to receive avelumab treatment is considered appropriate.

5.2.4 Justification of Open-label Study Design

The open-label study design is justified based on the following:

Double-blind controlled study would be impossible due to differences in treatment schedule and toxicity profile that would unmask treatment assignment.

5.2.5 Rationale for the Primary Endpoint

Overall survival was chosen as the primary endpoint because this is an unequivocal measurement of clinical benefit that will not be confounded by the open-label nature of the study.

Overall survival in PD-L1+ subjects was chosen as one of the primary objectives based on results from the EMR100070-001, Phase Ib, gastric primary cohort. In the group of GC/GEJC subjects who did not progress on or after first-line chemotherapy, a difference in median OS of 4.3 months was observed in subjects with PD-L1 tumor cells $\geq 1\%$ compared to the overall subjects.

5.2.6 Trial Periods

The study will consist of (i) Screening/baseline evaluation, (ii) induction, (iii) maintenance, and (iv) post-treatment follow-up period.

i) During Screening/baseline (Day -28 to Day 1), informed consent will be obtained and subject compliance with the inclusion/exclusion criteria will be ascertained.

ii) During the Induction Phase, subjects will receive 4 cycles of chemotherapy comprised of oxaliplatin and capecitabine every 3 weeks OR 6 cycles of chemotherapy comprised of oxaliplatin and 5-FU every 2 weeks.

Induction Chemotherapy:

Subjects enrolled in this trial will receive chemotherapy comprised of oxaliplatin and either 5-FU or capecitabine. Subjects who experience a CR, PR, or SD after 12 weeks will be randomly assigned to either avelumab or continuation of the same first-line chemotherapy they received during the Induction Phase. Subjects who demonstrate a response during the Induction Phase that renders their measurable disease no longer measurable at the time of the Maintenance Phase can be randomized.

iii) During the Maintenance Phase, subjects will be randomly assigned to receive either avelumab or continuation of the same chemotherapy regimen from the Induction Phase, until disease progression, unacceptable toxicity, or for the accepted maximal duration of the agent(s) selected.

Maintenance Avelumab Arm:

Subjects receiving avelumab will continue on-treatment until disease progression or unacceptable toxicity. Subjects receiving avelumab during the Maintenance Phase may continue treatment past the initial determination of disease progression according to RECIST v1.1 if they meet the criteria presented in Section 6.2.1 (Investigator-assessed benefit; tolerance of treatment; stable ECOG PS; and does not delay other imminent intervention).

Subjects receiving avelumab who have experienced a CR should be treated for a minimum of 12 months or until disease progression or unacceptable toxicity, after confirmation of response.

In case a subject with a confirmed CR relapses after stopping treatment, but prior to the end of the trial, 1 re-initiation of treatment is allowed at the discretion of the Investigator and after agreement with the Medical Monitor. In order to be eligible for retreatment, the subject must not have experienced any toxicity that led to treatment discontinuation of the initial avelumab therapy. Subjects who re-initiate treatment will stay on trial and will be treated and monitored according to the protocol.

Maintenance Chemotherapy Arm:

Maintenance chemotherapy will continue until disease progression or unacceptable toxicity or until the maximum acceptable dosing is achieved at the discretion of the Investigator.

Subjects who are not deemed eligible to receive further chemotherapy will receive BSC alone with no active therapy until disease progression. Prior to randomization, Investigators must specify BSC treatment for these subjects.

iv) The Follow-up Phase will include a post-treatment period and long-term follow-up visits. During the post-treatment period (from treatment discontinuation to Safety Follow-up), a Safety Follow-up visit will be scheduled 30 days after last treatment and a phone call will occur 90 days after treatment discontinuation.

A long-term follow-up visit will occur every 12 weeks for 5 years after the last subject receives the last dose of study drug (see Section 7.1.7 for details).

During Screening, induction, maintenance and post-treatment periods, subject will undergo visits and assessment procedures as per described in the Schedule of Assessments (Table 1 to Table 7).

5.2.7 Inclusion of Special Populations

Not applicable.

5.3 Selection of Trial Population

Only persons meeting all inclusion criteria and no exclusion criteria may be enrolled into the trial as subjects. Prior to performing any trial assessments not part of the subject's routine medical care, the Investigator will ensure that the subject or the subject's legal representative has provided written informed consent following the procedure described in Section 9.2.

5.3.1 Inclusion Criteria

For inclusion in the trial, all of the following inclusion criteria must be fulfilled:

1. Has read, understood and signed written informed consent before any trial-related procedure is undertaken that is not part of the standard subject management
2. Male or female subjects aged ≥ 18 years
3. Availability of a recently-obtained (within 6 months) biopsy from a non-irradiated area, formalin-fixed, paraffin-embedded (FFPE) block containing tumor tissue or a minimum

number of 10 (preferably 25) unstained tumor slides (cut within 1 week) suitable for PD-L1 expression assessment.

4. Disease must be measurable per RECIST v1.1
5. Subjects with histologically confirmed unresectable locally advanced or metastatic adenocarcinoma of the stomach or GEJ
6. ECOG PS of 0 to 1 at trial entry
7. Estimated life expectancy of more than 12 weeks
8. Adequate hematological function defined by white blood cell (WBC) count $\geq 2.5 \times 10^9/L$ with absolute neutrophil count (ANC) $\geq 1.5 \times 10^9/L$, lymphocyte count $\geq 0.5 \times 10^9/L$, platelet count $\geq 100 \times 10^9/L$, and hemoglobin ≥ 9 g/dL (may have been transfused).
9. Adequate hepatic function defined by a total bilirubin level $\leq 1.5 \times$ the upper limit of normal (ULN) range and aspartate aminotransferase (AST) and alanine aminotransferase (ALT) levels $\leq 2.5 \times$ ULN for all subjects
10. Adequate renal function defined by an estimated creatinine clearance ≥ 30 mL/min according to the Cockcroft-Gault formula (or local institutional standard method)
11. Negative blood pregnancy test at Screening for women of childbearing potential. For the purposes of this trial, women of childbearing potential are defined as: "All female subjects after puberty unless they are postmenopausal for at least 2 years, are surgically sterile, or are sexually inactive."
12. Highly effective contraception (ie, methods with a failure rate of less than 1 % per year) for both male and female subjects if the risk of conception exists (Note: The effects of the trial treatment on the developing human fetus are unknown; thus, women of childbearing potential and men must agree to use highly effective contraception, defined in [Appendix II](#) Guidance on Contraception or as stipulated in national or local guidelines. Highly effective contraception must be used 15 days prior to first trial treatment administration, and for the duration of trial treatment for all subjects. **Highly** effective contraception must be used at least for 60 days after stopping avelumab treatment and as indicated in the respective label [SmPC] for oxaliplatin, 5-FU or capecitabine for subjects receiving chemotherapy [in the Induction Phase and the Maintenance Phase], or as per label of any other therapy used as BSC. Should a woman become pregnant or suspect she is pregnant while she or her partner is participating in this trial, the treating physician should be informed immediately).

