7.1.1 Screening and Baseline Procedures and Assessments

The Screening procedures and Baseline assessments will be completed within 28 days before trial treatment starts.

During the Screening period and before any trial-related investigations and assessments are started, subjects will be asked to sign the ICF. The Screening procedures and Baseline assessments will be completed within 28 days of signing the ICF. Failure to establish eligibility within 28 days would result in screening failure and the subject will be excluded from the trial; however, subjects can be re-entered in the trial based on the Investigator's judgment and following Sponsor approval. In this case, a new ICF will be required to be signed by the subject.

The subjects' information that will be documented during Screening includes the demographic information (birth date, sex, and ethnicity) and the complete medical history, including the history of gastric cancer, previous and ongoing medications, and baseline medical condition (the information of concomitant medications and AEs and SAEs will be monitored throughout the trial treatment period). Moreover, an Emergency Medical Support card will be handed out at the Baseline assessments visit.

During Screening, subjects will undergo a complete physical examination, including recording body height and weight, vital signs, 12-lead ECG, and a determination of the ECOG PS (Table 1 and Table 2). The QoL questionnaires will be administered and completed by the subjects at baseline to collect baseline data about their health-related QoL.

The Screening laboratory examination includes hematology, hemostaseology, full serum chemistry, and full urinalysis (dipstick plus microscopic evaluation). Free thyroxine (T₄) and thyroid-stimulating hormone (TSH) will also be assessed at Screening for all subjects. The baseline CCI [REDACTED]

During Screening, a serum β -human chorionic gonadotropin (β -hCG) pregnancy test will be performed for females of childbearing potential (may be analyzed locally). HER2 testing (per local guidelines), blood HBV and HCV may be analyzed locally for all Screening subjects as these conditions are trial entry exclusion criteria (see Section 5.3.2). HBV surface antigen and anti-HCV tests must be performed at Screening to exclude subjects with hepatitis infection. If the anti-HCV

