test is positive, the infection must be confirmed by an HCV RNA test. Females who are postmenopausal (age-related amenorrhea ≥ 12 consecutive months and increased follicle-stimulating hormone [FSH] > 40 mIU/mL), or who have undergone hysterectomy or bilateral oophorectomy are exempt from pregnancy testing. If necessary to confirm postmenopausal status, FSH will be drawn at Screening.

The tumor evaluation (type and staging, etc.) will be performed using CT scan or MRI (if MRI is used, CT of chest is mandatory) as well as tumor markers or any other established methods (see Section 7.2.5 for details). A brain CT/MRI scan is required at Screening if not performed within 6 weeks prior to entering the Induction Phase. A bone scan should be done at Screening as clinically indicated.

Subjects are required to provide tumor tissue samples; see Section 7.6.1 for details. Tumor tissue collection will be done of a recently-obtained biopsy within 6 months from a non-irradiated area, FFPE block containing tumor tissue or a minimum number of 10 (preferably 25) unstained tumor slides suitable for PD-L1 expression assessment (cut within 1 week). Criteria for determining the adequacy of tumor tissue are described in the Study Manual.

Subjects who undergo a biopsy specifically as part of the Screening assessments for this protocol shall be permitted to participate in the protocol provided they meet all other inclusion criteria and no exclusion criteria. It is recommended that multiple biopsy samples should be collected, as feasible, for biomarker assessment to minimize inaccuracies in assessment due to tumor heterogeneity. The site pathologist shall review the Hematoxylin and Eosin stains when more than one FFPE block from a subject has been received. If from a resection specimen, the block that maximizes tumor content and tumor cell preservation should be tested by the central laboratory. If from biopsy specimen(s), all available tumor-containing blocks representing up to a maximum of 6 distinct biopsies, should be sent to the central laboratory as feasible.

The blood samples for baseline CCI, and CCI as well as for CCI assessments (optional) will be collected before or on Day 1 before trial treatment starts for subjects randomly assigned to receive avelumab.

CCI

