7.4.4 Vital Signs, Physical Examinations, and Other Assessments

Vital signs including body temperature, respiratory rate, heart rate (after 5-minute rest), and arterial blood pressure (after 5-minute rest) will be recorded at trial entry.

A complete physical examination (including general appearance, dermatological, head/neck, pulmonary, cardiovascular, gastrointestinal, genitourinary, lymphatic, musculoskeletal system, extremities, eyes [inspection and vision control], nose, throat, and neurologic status) will be performed at Screening and at subsequent visits as documented in the Schedule of Assessments and the results documented in the eCRF. Abnormal findings are to be reassessed at subsequent visits.

The ECOG PS will be documented during the Screening Phase and at each scheduled visit (if the Screening ECOG PS was performed within 3 days prior to Day 1, it does not have to be repeated at Day 1) and documented in the eCRF.

Body weight will be recorded at Screening and at subsequent visits as indicated in the Schedule of Assessments and documented in the eCRF. Height will be measured at Screening only.

A 12-lead ECG will be recorded as indicated in the Schedule of Assessments.

[figure not shown]
All newly diagnosed or worsening conditions, signs, and symptoms observed from Screening, whether related to trial treatment or not, are to be reported as AEs.

For female subjects of childbearing potential, a serum β -hCG pregnancy test will be carried out during the Screening Phase. A urine or serum β -hCG test will be performed at the visits as indicated in the Schedules of Assessments. Results of the most recent pregnancy test has to be available prior to the next dosing of trial treatment. Subjects who are postmenopausal (age-related amenorrhea ≥ 12 consecutive months and FSH > 40 mIU/mL), or who have undergone hysterectomy or bilateral oophorectomy are exempt from pregnancy testing.

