Appendix II Guidance on Contraception

BIRTH CONTROL METHODS CONSIDERED AS HIGHLY EFFECTIVE

According to the CTFG “Recommendations related to contraception and pregnancy testing in clinical trials” methods that can achieve a failure rate of less than 1% per year when used consistently and correctly are considered as highly effective birth control methods, such as:

- combined (estrogen and progesterone containing) hormonal contraception associated with inhibition of ovulation¹ (oral, intravaginal, transdermal)
- progesterone-only hormonal contraception associated with inhibition of ovulation¹ (oral, injectable, implantable²)
- intrauterine device (IUD)²
- intrauterine hormone-releasing system (IUS)²
- bilateral tubal occlusion²
- vasectomized partner^{2,3}
- sexual abstinence.⁴

¹ Hormonal contraception may be susceptible to interaction with the IMP, which may reduce the efficacy of the contraception method.

² Contraception methods in the context of this guidance are considered to have low user dependency.

³ Vasectomised partner is a highly effective birth control method provided that the partner is the sole sexual partner of the woman of childbearing potential trial participant and that the vasectomized partner has received medical assessment of the surgical success.

⁴ In the context of this guidance sexual abstinence is considered a highly effective method only if defined as refraining from heterosexual intercourse during the entire period of risk associated with the study treatments. The reliability of sexual abstinence needs to be evaluated in relation to the duration of the clinical trial and the preferred and usual lifestyle of the subject.

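### A sexually active, non-sterilized woman with 12 to under 24 months of amenorrhea and FSH above 40 mIU/mL needs a negative pregnancy test for entry, yet is exempt from pregnancy testing

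*Protocol*

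**What the plan says.** Inclusion criterion 11 (Protocol 5.3.1) sets the entry condition: "Negative blood pregnancy test at Screening for women of childbearing potential". For the purposes of the trial it counts as such "All female subjects after puberty unless they are postmenopausal for at least 2 years, are surgically sterile, or are sexually inactive". Section 5.3 makes every inclusion criterion mandatory.

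Section 7.1.1 orders the Screening serum test for the same group ("pregnancy test will be performed for females of childbearing potential (may be analyzed locally") and then lists who is exempt: "Females who are postmenopausal (age-related amenorrhea ≥ 12 consecutive months and increased follicle-stimulating hormone [FSH] > 40 mIU/mL"), together with women who have had a hysterectomy or bilateral oophorectomy. FSH is drawn at Screening only where it is needed to confirm postmenopausal status.

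Section 7.4.4 repeats the exemption, both for these two operations and for menopause, which it words as "postmenopausal (age-related amenorrhea ≥ 12 consecutive months and FSH > 40 mIU/mL"). The same section requires the most recent pregnancy result to be available before the next dose.

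Neither the criterion nor the two procedural sections refer to each other on this point, and none states an order of precedence.

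**The concern.** The entry criterion and the testing exemption use different markers for the end of childbearing potential: 2 years past menopause in one, 12 months of amenorrhea plus an FSH value in the other. For a woman between the two markers, a site that follows 7.1.1 omits a test that inclusion 11 requires. Inclusion 12 calls the effects of trial treatment on the fetus unknown, so this is a safety matter even though it touches few women.

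Maintenance enrollment is complete, so the entry test itself is largely past. The exemption in 7.4.4 also applies to the repeat tests in Maintenance, however, so it still matters for women on treatment. It also affects reporting. SAP Appendix I has deviation codes for enrolling or randomizing (LABPRCO01) and for dosing (LABPRCO02) without all safety laboratory results, the pregnancy test included. The same missing test is a deviation under inclusion 11 and compliant under 7.1.1 and 7.4.4.

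**Working it through.** The plan states no figure to reproduce. The check applies both rules to the same women.

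**Rules**

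- Test needed for entry (5.3.1, no. 11): post-pubertal, and not postmenopausal for 2 years or more, not surgically sterile, not sexually inactive.
- Exempt from testing (7.1.1 and 7.4.4): amenorrhea of 12 months or more *and* FSH above 40 mIU/mL; or hysterectomy; or bilateral oophorectomy.
- Tests are ordered only for women of childbearing potential (7.1.1 to 7.1.4, 7.1.6, 7.4.4).

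**Test cases**

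| Woman | Inclusion 11 | Exemption | Result |
|---|---|---|---|
| Amenorrhea 18 months, FSH 50, sexually active, not sterilized | Childbearing potential; negative test required | Exempt | Direct conflict |
| Amenorrhea 3 years, FSH 35 | Not of childbearing potential; no test ordered | Wording not met | No conflict; she needs no exemption |
| Sexually inactive | Not of childbearing potential; no test ordered | Not listed | No conflict |
| Tubal occlusion | Depends on the undefined term *surgically sterile* | Not listed | Ambiguity |

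Only the first case is a contradiction.

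**Width of the window**

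- If the 2 years run from the last period: months 12 to 24 of amenorrhea, 24 − 12 = 12 months.
- If they run from the date the 12-month criterion is met: the upper end is 12 + 24 = month 36, so 36 − 12 = 24 months.

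The conflict exists on either reading.

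**Number affected (illustrative)**

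The only documented input is 499 randomized subjects (Protocol 8.1). The other inputs are assumptions: 30 to 40% women, and 1 to 3% of those women with 12 to under 24 months of amenorrhea.

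- Women: 0.30 × 499 = 149.7 and 0.40 × 499 = 199.6, about 150 to 200.
- In the window: 150 × 0.01 = 1.5; 200 × 0.03 = 6.

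This is an upper range for those assumptions, because the FSH and sexual-activity conditions have not been applied. It refers to randomized subjects and to the 12-month window. The Induction population, to which the Screening test applies, is larger, and the documents give no count for it.

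**The case against.** The strongest reply is that inclusion 11 is the only definition of childbearing potential in the protocol, and that 7.1.1 and 7.4.4 merely describe postmenopausal status for a testing exemption. An exemption does not forbid a test. Sections 5.3 and 5.4 require every criterion to be met and verified, so a careful site would test the woman anyway. Other safeguards exist: pregnancy is an exclusion criterion (5.3.2, no. 15), and treatment stops at once if pregnancy occurs (7.4.2). With enrollment complete, few women remain exposed to the inconsistency.

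Much of this stands and limits the point. It does not remove it: a site that relies on the exemption is also following the protocol, and nothing tells it that inclusion 11 takes priority.

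A reader might infer more than the texts support:

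- *That the rules conflict in both directions.* They do not. A woman outside the inclusion 11 definition is never in the group for whom tests are ordered, so failing to meet the exemption has no effect.
- *That Appendix II contradicts inclusion 11 on abstinence.* Appendix II says "In the context of this guidance sexual abstinence is considered a highly effective method only if defined as refraining from heterosexual intercourse" during the whole risk period. That describes a contraceptive method; it does not bring a sexually inactive woman back into pregnancy testing.
- *That contraception, or deviation code PROCED08, is affected.* Sections 7.1.1 and 7.4.4 exempt from testing only. Contraception is set by inclusion 12, and the woman in the conflict window remains subject to it.
- *That the efficacy analysis is affected.* LABPRCO01 and LABPRCO02 are not marked clinically important in SAP Appendix I, and a missing pregnancy test is not among the Per-Protocol exclusions in SAP Section 9.

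**Conclusion.** The contradiction is real and narrow. It concerns sexually active, non-sterilized women with amenorrhea of 12 to under 24 months and FSH above 40 mIU/mL. It affects the Screening test, repeat testing before dosing, and the coding of missing tests as deviations. On the assumptions stated, at most about 1.5 to 6 randomized women are involved; if the 2 years are counted from the date menopause is established, the window is twice as wide and the assumed share would have to be reconsidered. The existence of the conflict follows from the text alone; its size is assumption.

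Separately, *surgically sterile* in inclusion 11 is not aligned with the two operations named in the exemption. That is an unclear term, not a contradiction. Alpha, power and the efficacy analysis sets are unaffected. This is a minor safety and consistency correction.

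**What to change.** Reconcile inclusion 11 with 7.1.1 and 7.4.4 so that a single criterion governs both the entry test and the exemption from testing, state it once, and cross-refer to it from each section. At the same time, state which procedures count as surgical sterility. The sponsor's medical team must decide which threshold stands; this review takes no view on it. The SAP codes LABPRCO01 and LABPRCO02 can then be assigned against that one criterion.

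The cost is a written amendment under Protocol 10.5, with authority and ethics review if it is classed as major, distributed to about 230 sites. Depending on the threshold chosen, a few more pregnancy tests may follow. Because the remaining effect is on women still being treated, the change could be carried with another amendment if one is already planned.
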